4.2 Exclusion criteria

- A history of hypersensitivity / contraindication to one of the drugs administered or to their ingredients or to drugs with a similar chemical structure.
- Other methods of hallux valgus surgery and additional surgeries of the little toes other than those mentioned.
- Neurological disorder that affects the sensory-motor function.
- Refusing to participate in the study or refusal of consent to study.
- Existing pregnancy.
- Surgery on the same leg within the last month.
- Surgeries with general anaesthesia.

5 Trial medication

5.1 Description of trial medication (cf. also specialist information)

- Agent: ropivacaine 0.2 %
- Trade name: Ropinaest® 2 mg/ml

- Manufacturer: Gebro GmbH, 6391 Fieberbrunn, Austria
- Ingredients: The agent is: ropivacaine hydrochloride. Ropinaest® 2 mg/ml contains 2 mg of ropivacaine hydrochloride per ml solution (in the form of ropivacaine hydrochloride 1 H₂O). Further components are: sodium chloride, hydrochloric acid and sodium hydroxide for pH regulation, water for the purpose of injection.
- Packaging: Naropin is a clear, colorless solution for injection. 10 ml and 20 ml ampoules of polypropylene in sterile blister packs with 5 pieces or 5x5 pieces (hospital pack).
- Storage: Keep the medicinal product out of the sight and reach of children. The medicinal product may not be used after the expiry date stated on the label and the carton. The expiry date refers to the last day of the indicated month. Do not store at temperatures above 25°C. Do not freeze. Normally, Ropinaest is stored at your doctor's practice or at the hospital. They are also responsible for the quality of the product if it is opened but not immediately used. The medicinal product must be visually inspected before use. The solution shall only be used if it is clear and practically free of particles and if the container is not damaged. They are also responsible for the right disposal of any Ropinaest that has not been used.
- Shelf life: From a microbiological point of view, the product shall be applied immediately after opening. If it is not applied immediately, the user – before using the medicinal product – is responsible for the duration and conditions of storage after opening which, in general, should not exceed 24 hours at 2 – 8°C.
- Precautions, incompatibilities: ropivacaine infusion solution is chemically and physically compatible with: Fentanyl citrate, sufentanil citrate, morphine sulfate, clonidine hydrochloride. From a microbiological point of view, mixtures should be used immediately. If they are not used immediately, the user – before using the medicinal product – is responsible for the duration and conditions of storage after opening which, in general, should not exceed 24 hours at 2 – 8°C.

5.2 List of side effects and interactions

The side-effect profile of ropivacaine is similar to the side-effect profile of other long-acting local anaesthetics of the amide type. Side effects are to be distinguished from physiological effects caused by the block anaesthesia itself (e.g. decrease of blood pressure and bradycardia during spinal/epidural anaesthesia).

Very frequently (> 1/10)

- Angiopathies: hypotension
- Disorders of the gastro-intestinal tract: nausea

Frequently (> 1/100)

- Diseases of the nervous system: headache, paraesthesia, daze Cardiac diseases: bradycardia, tachycardia
- Angiopathies: hypertonia
- Diseases of the gastro-intestinal tract: vomiting^b

- Diseases of the kidney and urinary tract: urinary retention
- General disorders and administration site conditions: rise in temperature, rigor, back pain

Occasionally (> 1/1000)

- Psychiatric disorders: fearfulness
- Diseases of the nervous system: symptoms of a CNS toxicity (convulsions, grand mal type convulsions, epileptic seizures, daze, perioral paraesthesia, numbness of the tongue, hyperacusis, tinnitus, visual impairment, dysarthria, muscle twitching, tremor)**, hypoesthesia
- Angiopathies: syncope
- Diseases of the respiratory tract, chest and mediastinum: dyspnoea
- General disorders and administration site conditions: hypothermia

Rare (< 1/1000)

- Cardiac diseases: cardiac arrest, cardiac dysrhythmias
- General disorders and administration site conditions: allergic reactions (anaphylactic reactions, angioneurotic oedema and urticaria)

Acute systemic toxicity

Systemic toxic reactions mainly affect the central nervous system (CNS) and the cardiovascular system (CVS). Such reactions are caused by high blood concentrations of a local anaesthetic which may occur following (unintended) intravascular injection, overdosage or unusually quick absorption in highly vascularized areas. CNS reactions are similar in all amide-type local anaesthetics, whereas cardiac reactions rather depend on the agent as far as quantity as well as quality are concerned.

CNS toxicity

CNS toxicity reactions occur gradually with signs and symptoms of increasing severity. Early symptoms such as visual and hearing impairments, perioral numbness, vertigo, light dizziness, tingling and paraesthesiae are observed. Dysarthria, muscle rigidity and muscle twitching are more severe and may indicate the onset of generalized convulsions. These signs may not be falsely interpreted as neurotic behaviour. Unconsciousness and grand mal may follow which may last from a few seconds to several minutes. During the convulsions, hypoxia and hypercapnia, together with a breathing disturbance, quickly occur due to the increased muscular activity. In severe cases even apnoea may occur. Respiratory and metabolic acidosis increases and prolongs the toxic effects of the local anaesthetics. Improvement occurs after redistribution of the local anaesthetic from the central nervous system and the ensuing metabolism and elimination. Improvement can occur quickly if no great dosages of the medicinal product were injected.

Toxicity to the cardiovascular system

Cardiovascular toxicity proves to be a more serious condition. Hypotension, bradycardia, arrhythmia and even cardiac arrest may occur as a result of high systemic concentrations of the local anaesthetic. I. v. infusion of ropivacaine in subjects caused a reduction in impulse conduction and

contractility. In general, toxic effects to the cardiovascular system are first manifested with CNS toxicity symptoms, except for when the patient receives general anaesthesia or if he/she is profoundly sedated with substances such as benzodiazepines or barbiturates.

5.3 Placebo, comparator product

- Agent: sodium chloride 0.9 %
- Trade name: physiological saline solution “Fresenius”
- Manufacturer: Fresenius Kabi Austria GmbH [name], Austria
- Ingredients: the agent is: sodium chloride. The other components are: hydrochloric acid, sodium hydroxide, water for injection purposes.
- Packaging: physiological saline solution “Fresenius” is a clear and colorless infusion solution, available in glass bottles, polyethylene bottles, polypropylene bottles, intravenous bags, vials, polyethylene ampoules and polypropylene ampoules.

5.4 Randomization

Randomization takes place in 2 groups as balanced randomization by means of a computer-generated random number sequence. This random number sequence is generated with the help of the website www.random.org (numbers, random sequence generator). The first 25 results are assigned to the verum group, the other 25 results are assigned to the placebo group. Upon admission to the study, the patients receive at random one of these numbers which are contained in sealed envelopes on which the numbers 1 to 50 are written. The randomization envelope is opened by an independent member of the nursing staff – who is not involved in the further treatment of the patient – several minutes prior to the start of surgery. Such member will fill a 50 ml perfusor syringe with either ropivacaine 0.2 % or physiological saline solution. The patients, surgeons as well as the care-taking nursing staff are blinded as regards the content. The deciphering list will only be opened after conclusion of the last follow-up examination.

5.5 Treatment scheme

5.5.1 Administration instructions

At the end of every patient's surgery, a pain catheter (InfiltraLong Katheter 19G x 420mm, Pajunk Medizintechnologie GmbH) is placed in the surgical wound through which ropivacaine 0.2 % (verum) or NaCl 0.9 % (placebo) is continuously administered at a rate of 2 ml/h during the first 24 postsurgical hours via a syringe pump. The catheter is removed on the following day in the course of the routine change of dressing.

As for standard pain treatment (Non Investigational Medicinal Product, NIMP), the patients receive naproxen 500 mg (Naprobene®, ratiopharm Arzneimittel Vertriebs-GmbH, Wien, Austria) p.o. in the morning and in the evening from day 1 to 8 as well as hydromorphone 2.6 mg (Hydal®, Mundipharma Ges.m.b.H., Austria) p.o. in case of VRS > 3 (every 4 hours at maximum) from day 1 to 3.

5.5.2 Emergency measures

In the unlikely case that an allergic reaction or signs of a systemic toxicity occur(s), the supply of the trial substance is interrupted immediately and emergency treatment in accordance with the responsible doctor is provided.

5.5.3 Concomitant medication

As for standard pain treatment (NIMP), the patients receive naproxen 500 mg (Naprobene®, ratiopharm Arzneimittel Vertriebs-GmbH, Wien, Austria) p.o. in the morning and in the evening as well as hydromorphone 2.6 mg (Hydal®, Mundipharma Ges.m.b.H., Austria) p.o. in case of VRS > 3 (every 4 hours at maximum) in the course of their stay in hospital. After discharge on the 2nd day following surgery, the patient is prescribed naproxen 500 mg 2x each day for 5 days.

5.6 Storing, issuing and taking back as well as documenting the trial medication (drug accountability)

The trial medication is provided by the nursing staff of the pain outpatient department of the University Hospital of Innsbruck. The investigator is responsible for issuing, taking back and documenting the trial medication in the trial center. The trial medication (including the pain catheters used) may only be used in the framework of this study and may not be used after its expiry date. Issuing and taking back the trial medication is documented in the Drug Accountability Log in the investigator site file (identification of patient, date and amount of medication issued). Upon receipt of the trial medication, the patients are to be carefully informed on how to use the trial medication.

5.7 Compliance

The continuous administration of the trial substance is ensured by the syringe pump catheter system and observed by the nursing staff.

5.8 Blinding and emergency envelopes

5.8.1 Blinding

The patients are assigned to one of the 2 treatment groups by means of random, computer-generated numbers which are contained in sealed envelopes on which the numbers 1-50 are written. The envelopes are provided by the investigator. The randomization envelope is opened by an independent member of the nursing staff – who is not involved in the further treatment of the patient – several minutes prior to the start of surgery. Such nursing staff of the pain outpatient department of the University Hospital of Innsbruck prepares the trial substance in a perfusor syringe and hands it over to the surgical nursing staff.

5.8.2 Emergency envelopes

Emergency envelopes for the identification of the trial substance are deposited at the ward's head of the respective care-taking station and are only opened in case of a probable vital threat caused by the trial substance.

5.8.3 Premature unblinding

Unblinding only takes place in case of a vital threat caused by the trial substance.

5.8.4 Regular unblinding

Regular unblinding only takes place after conclusion of the last follow-up examination including documentation.

6 Course of study

See also visit plan. On the day of hospitalization (visit 1, baseline, day 0) for hallux valgus surgery, the measures mentioned under point 6.1 are carried out as part of informing the patient on the surgery. On day 1, hallux valgus surgery is performed under local anaesthesia, at the end of the surgery the pain catheter (InfiltraLong-Katheter 19G x 420mm, Pajunk Medizintechnologie GmbH) is inserted to allow for continuous wound infiltration with ropivacaine 0.2 % or with physiological saline solution. After surgery, the care-taking nursing staff of the respective ward documents the pain level under continuous wound infiltration and standard pain treatment every 4 hours via VRS (visit 2, see point 6.2). On day 2 (first postsurgical day), the pain catheter is removed in the course of the first routine change of dressing during morning visit (approx. 07.30 a.m.). Under standard pain treatment, the care-taking nursing staff continues to document the pain level every 4 hours via VPRS. On day 3 (second postsurgical day), the patient is discharged from hospital. He/she receives a prescription for the intended pain medication as well as further follow-up appointments in 1 (visit 3), 2 (visit 4) and 6 weeks (visit 5). In the course of these outpatient postsurgical follow-ups, the examinations described under points 6.3 to 6.5 are carried out and AEs and SAEs are recorded. Visit 5 (outpatient 6 weeks follow-up) represents the end of the study's follow-up period. After conclusion of the study, the examining doctor decides on further outpatient follow-ups.

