9.2 Audit

In order to guarantee that the trial is conducted pursuant to GCP guidelines, internal (e.g. by the sponsor) and external (e.g. by the authorities) audits may be conducted. The auditor is independent vis-à-vis the employees who are involved in the trial.

During the audit, the following points are checked, amongst others:

- conduction of the trial according to the study protocol
- validity of data
- quality of trial pursuant to GCP guidelines.

Following every external audit, the investigator receives an audit confirmation by the auditor. This confirmation must be kept in the investigator site file in order to have it at disposal in case of an inspection by the authorities. The audit report is transmitted to the study sponsor. At the end of the trial, an audit certificate is enclosed to the final report. In addition, authorities may conduct audits and inspections pursuant to the Austrian Medicinal Product Act.

10 Data entry and data management

Study with paper-based documentation

Data is managed and processed by the data manager by means of the software SPSS Statistics (company IBM, Armonk, New York, USA) and Excel (company Microsoft, Redmond, WA, USA).

Data is validated by the programmed range, validity and consistency checks. Additionally, there is a manual/visual check for medical plausibility pursuant to the requirements of GCP. If necessary, queries may occur which are to be transmitted to the respective trial center on special forms. On the basis of the forms, the investigator has to review and answer those discrepancies. These forms are then returned to data management where those discrepancies are corrected in the database accordingly. The forms are stored together with the case report form at the trial center and by data management.

Upon study completion, the database is closed after all entries have been entered and all queries have been resolved. This process is documented.

11 Statistics

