11.3.2 Definition of analysis sets

The intent-to-treat population to be analysed includes all randomized patients to whom the trial medication has been given. The statistical analysis of this set decides on the statement statistically significant or not statistically significant. The per protocol population is also analysed, i.e. those patients for whom no major protocol deviations have occurred.

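### Regular unblinding is tied to the last follow-up and not to database closure, so late data corrections and per-protocol exclusions may be settled with the allocation known

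*Combined protocol and SAP*

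**What the plan says.** Three places fix the time of regular unblinding. Section 5.8.4: "Regular unblinding only takes place after conclusion of the last follow-up examination including documentation". Section 5.4: "The deciphering list will only be opened after conclusion of the last follow-up examination". Section 11.2 repeats the sentence from 5.4. Emergency unblinding is handled separately in 5.8.2 and 5.8.3.

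Section 10 describes data handling as its own sequence. Documentation is on paper and the data are processed in SPSS and Excel. There are programmed checks, and "Additionally, there is a manual/visual check for medical plausibility pursuant to the requirements of GCP". Queries go back to the centre on forms: "On the basis of the forms, the investigator has to review and answer those discrepancies". Data management then corrects the database. The sequence ends with: "Upon study completion, the database is closed after all entries have been entered and all queries have been resolved". The synopsis and section 3.5 equate study completion with the last patient's last visit.

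Section 11.3.2 defines the intention-to-treat set as the randomized patients who were given trial medication, and says of it: "The statistical analysis of this set decides on the statement statistically significant or not statistically significant". It then adds: "The per protocol population is also analysed, i.e. those patients for whom no major protocol deviations have occurred". It does not define a major deviation, and it does not say who classifies deviations, when, or whether this is done blind.

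Sections 5.4 and 11.2 name the patients, surgeons and ward nurses as blinded, and 6.6.1 repeats this for the nurses who collect the pain ratings. The data manager and the analyst are not named.

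**The concern.** Blinding protects the data while they are collected, and also while they are cleaned and while patients are assigned to analysis sets. The primary endpoint is a subjective 0 to 10 rating, recorded on the ward and transferred to paper forms. Some queries call for judgement, and so does calling a deviation major.

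The unblinding rule is linked to a clinical event, the last follow-up. It has no link to the data events that should come before it. A centre could comply fully with 5.8.4 and still have queries open, and per-protocol membership undecided, when the list is opened. The investigator answers the queries (section 10) and also carries out the analysis (12.1), so one role could be both informed and in a position to influence the data. At stake are any primary pain scores still under query and the credibility of the per-protocol analysis.

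**Working it through.** **1. Order of events.** The sections side by side:

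- Earliest time for opening the list: the last follow-up (5.4, 11.2), with that examination documented (5.8.4).
- Database closure: on study completion, which is the last patient's last visit (synopsis, 3.5), and then only once entry is finished and queries are resolved (section 10).
- Classification of deviations: no time given (11.3.2).

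Unblinding and closure are thus tied to the same event. Closure carries the further condition that queries are resolved; unblinding does not. Opening the list first is allowed. So is opening it afterwards, because 5.8.4 sets only an earliest time.

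**2. What could still be open.** Section 10 gives a time for closure only, not for entry or queries. The 48-hour ratings end on about day 3 and the final visit is on day 42 (6.5), so each patient has about 42 − 3 = 39 days in which those ratings could be entered and queried before the last visit. (The visit plan heads the same visit day 24, which would give 24 − 3 = 21 days.) Much may be settled by then, but nothing requires it.

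**3. Planning figures.** The plan gives no figure on this point. The inputs used below are the planned difference of 1 and SD of 1 (11.1). Those assumptions reproduce the plan's own sample size: a two-sided 5% t-test with power 80% gives 16.71, so 17 per group and 34 in total (power 0.807). Both stated group sizes are shown, 25 (3.4) and 20 (11.1).

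**4. Per-protocol route (supporting analysis only).** Removing m patients who lie c SD above the mean of an arm of n shifts that mean by m × c × SD / (n − m). With the assumed m = 2 and c = 2:

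- n = 25: 2 × 2 × 1 / 23 = 0.174 points, 17% of the planned difference.
- n = 20: 2 × 2 × 1 / 18 = 0.222 points, 22%.

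This is a chosen scenario. If scores are normal, 0.02275 of patients lie above +2 SD. The chance of at least two such patients in a given arm is 1 − 0.97725^25 − 25 × 0.02275 × 0.97725^24 = 0.11 for n = 25, and by the same formula 0.075 for n = 20. Both patients would also have to be classifiable as major deviators.

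**5. Data-correction route (can reach the intention-to-treat result).** Ratings every 4 hours over 48 hours give 48 / 4 = 12 per patient, or 12 × 50 = 600 for 50 patients. Suppose one reading is changed by k points. The mean of the patients' averages in that arm shifts by k / (12 × n). The mean of the maxima shifts by at most k / n, which happens when the changed reading sets that patient's maximum. For k = 1 up to the full scale of 10:

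| | n = 25 | n = 20 |
|---|---|---|
| Average score | 0.003 to 0.033 | 0.004 to 0.042 |
| Maximum score | up to 0.04 to 0.4 | up to 0.05 to 0.5 |

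Matching the 0.174 shift of step 4 on the average score would take net corrections of 0.174 × 300 = 52 points in one arm of 25. The maximum is about 12 times as sensitive to a single reading. If fewer than 12 ratings are available, the shift in the average grows in proportion. The documents do not say how many readings would be queried.

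**The case against.** The strongest reply is that the declared result is largely protected. The intention-to-treat analysis decides significance, and its membership rule (randomized and given medication) leaves little room for choice. This stands. A reader might infer that unblinded per-protocol exclusions could turn the trial's conclusion; 11.3.2 rules that out.

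Several other replies also stand:

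- A reader might infer that all cleaning follows unblinding. The documents do not say so. Section 8.1 requires prompt entry on the forms and has the monitor check pages for plausibility and completeness; 9.1 provides for monitoring at set intervals and source data verification.
- Corrections leave a trail: old entries stay legible and changes are signed and dated (8.1).
- Section 12.1 read alone suggests that the investigator analyses unsupervised. Section 11.1 puts planning and analysis under the biometrician's direction.
- No deviation rate is given, so nothing supports a claim that deviations will be common. Hydromorphone above the stated pain threshold and catheter removal at the morning visit are part of the written scheme (5.5.1, 6.2) and are not deviations in themselves.
- The last follow-up could be read as each patient's own. There is one list, and opening it after one patient's visit would unblind others still in follow-up, so the natural reading is the trial's last examination.

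One reply is weaker. The documentation condition in 5.8.4 might be read to cover cleaned data. Documentation (section 8) and data management (section 10) are separate sections, nothing equates them, and 5.4 and 11.2 omit the condition. None of these replies supplies the missing link between unblinding and closure.

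**Conclusion.** The point holds as a gap in the order of procedures. The plan allows regular unblinding before queries are resolved, before the database is closed and before per-protocol membership is settled. It does not require that order, and the documents do not show that it happened.

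The exposure is moderate. Per-protocol exclusions affect only the supporting analysis; the 0.17 and 0.22 point shifts are arithmetically right for a constructed and fairly unlikely case. The primary result can be reached only through corrections made after unblinding. On the average score a single correction is nearly harmless. On the maximum score, which is also a primary variable (11.3.1), a few corrections could be visible. Section 11.1 states a relevant difference for the average only, so there is no planned figure against which to judge a shift in the maximum.

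These sizes assume an SD of 1, complete 4-hourly ratings and equal arms of 25 or 20. How many corrections would fall after unblinding cannot be derived from the documents. The change is worth making because it removes the question at almost no cost.

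**What to change.** Give 5.4, 5.8.4 and 11.2 one common rule: the deciphering list is opened only after (a) the last follow-up of the last patient, (b) closure of the database under section 10 with all queries resolved, and (c) filing of a dated record that assigns each patient to the intention-to-treat and per-protocol sets. Emergency unblinding under 5.8.2 and 5.8.3 stays as it is.

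The cost is that unblinding happens somewhat later, by the time needed to finish queries and closure (the documents give no figure), and that one additional record is filed. The new order makes the per-protocol classification blind but does not define a major deviation. A definition in 11.3.2 would reduce the remaining discretion and could be added in the same amendment.
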